4.2 Indication to be Studied

Enrolling subjects must have Type 1 diabetes mellitus for more than 5 years, present with normal kidney function and have metabolic lability despite optimal intensive insulin management efforts. The enrollment inclusion and exclusion criteria for recipients and donors are discussed in more detail in Section 6.4 *Study Population*.

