6.4.1 Recipient Inclusion Criteria

Enrolling subjects must have Type 1 diabetes mellitus for more than 5 years, complicated by the following situations that persist despite intensive insulin management efforts (Appendix *Pre-Screening*):

- a. At least one episode of severe hypoglycemia in the past 3 years defined as an event with symptoms compatible with hypoglycemia in which the subject required the assistance of another person, and which was associated with either a blood glucose level < 50 mg/dL (2.8 mmol/L) or prompt recovery after oral carbohydrate, intravenous glucose, or glucagon administration
- b. Reduced awareness of hypoglycemia, as defined by the absence of adequate autonomic symptoms at capillary glucose levels of < 54 mg/dL (3 mmol/L as reported by the subject

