## 9.2. Analysis of Secondary Endpoints

Except for the primary analyses there are no explicit or implied hypotheses in the protocol. Changes in the secondary outcomes are of interest as they will relate to efficacy as measured by the primary outcome variable. All the secondary endpoints will be evaluated at 1 year after the first and 1 year after the last transplant, respectively, with the day of corresponding transplant always designated Day 0.

We will evaluate the proportions of patients presenting with insulin independence among all patients and among the patients who fulfilled the primary endpoint, respectively. **Insulin independence** while fulfilling the primary endpoint will be further evaluated by the following parameters:

- Absence of exogenous insulin injection reported at Day 365.
- Fasting capillary glucose level not exceeding 140 mg/dL (7.8 mmol/L) more than three times in a week (based on measuring capillary glucose levels a minimum of 7 times in a seven day period) at Day 365 ± 28 days.
- Fasting plasma glucose level ≤ 126 mg/dL (7.0 mmol/L) at Day 365 ± 28 days (if the fasting plasma glucose level is > 126 mg/dL [7.0 mmol/L], it must be confirmed in an additional one out of two measurements).
- 2-hour postprandial capillary glucose not exceeding 180 mg/dl (10.0 mmol/L) more than one out of every seven times in a week (based on measuring capillary glucose levels a minimum of 7 times in a seven day period) at Day 365 ± 28 days.
- Evidence of endogenous insulin production defined as fasting or stimulated C-peptide levels ≥ 0.5 ng/mL (0.16 nmol/L) at Day 365 ± 28 days.

Number and percent (over the total number of patients attaining primary endpoint) of patients attaining each outcome listed above will be summarized.

**Hypoglycemic episodes** will be measured by the Ryan HYPO Score (Ryan et al., 2004) derived from the number and severity of hypoglycemic episodes recorded throughout the follow-up phase from Day 28 to Day 365. Additionally the percent reduction from baseline will be reported.

**Glucose variability and hypoglycemia duration will be measured by continuous glucose monitoring system (CGMS)** for a 3-day period at three different time points: 1) at screening, 2) one year after first islet transplant, and 3) one year after last islet transplant. The following measurements and analysis will be reported:

- Mean glucose concentration
- Percent of time in the following ranges:
  - < 60 mg/dl
  - 60-140 mg/dl
  - 141-200 mg/dl

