Among patients fulfilling the primary efficacy outcome (N=X):				
Absence of exogenous insulin	X (XX)	X (XX)	X (XX)	X (XX)
Fasting capillary glucose in a week:				
Not exceeding 140 mg/dL more than 3X	X (XX)	X (XX)	X (XX)	X (XX)
Fasting plasma glucose $\leq$ 126 mg/dL	X (XX)	X (XX)	X (XX)	X (XX)
Postprandial capillary glucose in a week:				
Not exceeding 180 mg/dl more than 1X/7X	X (XX)	X (XX)	X (XX)	X (XX)
C-peptide (fasting or stimulated) $\geq$ 0.5 ng/mL	X (XX)	X (XX)	X (XX)	X (XX)

XXXXXXXXXX.sas, DDMMYYYY:HHMM

TABLE 14.2.2b  
 Summary of Secondary Efficacy Endpoints:  
 Patients' HYPO Score at 1 Year after First and Last Transplant

ITT population (N=X)		n	Mean	SD	Median	Minimum	Maximum	Missing n (%)
HYPO	Baseline (pre-Tx):	X	XX	XX	XX	XX	XX	X (XX)
	First Tx Day 365 % Reduction from baseline	X	XX	XX	XX	XX	XX	X (XX)
	Last Tx Day 365 % Reduction from baseline	X	XX	XX	XX	XX	XX	X (XX)

XXXXXXXXXXXX.sas, DDMMYYYY:HHMM

TABLE 14.2.2c  
 Summary of Secondary Efficacy Endpoints:

Patients' Glucose Variability and Hypoglycemia Duration at 1 Year after First and Last Transplant

ITT population (N=X)		n	Mean	SD	Median	Minimum	Maximum	Missing n (%)
Baseline	Mean Glucose	X	XX	XX	XX	XX	XX	X (XX)
	Percent time in range:							
	< 60 mg/dl	X	XX	XX	XX	XX	XX	X (XX)
	60-140 mg/dl	X	XX	XX	XX	XX	XX	X (XX)
	141-200 mg/dl	X	XX	XX	XX	XX	XX	X (XX)
	> 200 mg/dl	X	XX	XX	XX	XX	XX	X (XX)
First Tx Day 365	Mean Glucose	X	XX	XX	XX	XX	XX	X (XX)
	Percent time in range:							
	< 60 mg/dl	X	XX	XX	XX	XX	XX	X (XX)
	60-140 mg/dl	X	XX	XX	XX	XX	XX	X (XX)
	141-200 mg/dl	X	XX	XX	XX	XX	XX	X (XX)
	> 200 mg/dl	X	XX	XX	XX	XX	XX	X (XX)
Last Tx Day 365	Mean Glucose	X	XX	XX	XX	XX	XX	X (XX)
	Percent time in range:							
	< 60 mg/dl	X	XX	XX	XX	XX	XX	X (XX)
	60-140 mg/dl	X	XX	XX	XX	XX	XX	X (XX)
	141-200 mg/dl	X	XX	XX	XX	XX	XX	X (XX)
	> 200 mg/dl	X	XX	XX	XX	XX	XX	X (XX)

Note: Baseline levels were measured prior to the initial transplant.

XXXXXXXXXX.sas, DDMMYYYY:HHMM

TABLE 14.3.1  
 Overall Summary of Treatment-Emergent Adverse Events

Type of AE	# of Islet Transplantations Received			
	Total [1] (N=X)	1 Tx (N=X)	2 Tx's (N=X)	3 Tx's (N=X)
TEAEs				
Events	X	X	X	X
Patients: n(%)	X (XX%)	X (XX%)	X (XX%)	X (XX%)
Serious TEAEs				
Events	X	X	X	X
Patients: n(%)	X (XX%)	X (XX%)	X (XX%)	X (XX%)
TEAEs leading to discontinuation				
Events	X	X	X	X
Patients: n(%)	X (XX%)	X (XX%)	X (XX%)	X (XX%)
TEAEs with an outcome of death				
Events	X	X	X	X
Patients: n(%)	X (XX%)	X (XX%)	X (XX%)	X (XX%)

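### The secondary endpoint named glucose variability has no statistic that directly measures variability within a patient

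*SAP*

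**What the plan says.** The third secondary efficacy endpoint, in Protocol 6.10.2 and SAP 2.7.2 and 9.2, reads: "Glucose variability and hypoglycemia duration will be measured by continuous glucose monitoring system (CGMS"). The recording is made "for a 3-day period at three different time points": screening, one year after the first transplant and one year after the last. Two kinds of output follow. One is "Mean glucose concentration". The other is "Percent of time in the following ranges", with cut-points giving below 60, 60-140, 141-200 and above 200 mg/dL.

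The shell for Table 14.2.2c in SAP 14 is titled "Patients' Glucose Variability and Hypoglycemia Duration at 1 Year after First and Last Transplant". At each of the three time points it has five rows: mean glucose and the four ranges. Its columns are n, mean, SD, median, minimum, maximum and missing, taken across patients. It has no row for change from screening.

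On the population, Protocol 4.2 says that subjects must "have metabolic lability despite optimal intensive insulin management efforts" and refers to Section 6.4 for the detailed criteria.

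**The concern.** The endpoint's name has two halves. Percent of time below 60 mg/dL answers the hypoglycemia-duration half. Nothing in the list directly answers the variability half: neither document specifies a within-patient SD, a coefficient of variation (CV) or a lability index. The SD column could be mistaken for one, but it describes how patients differ from each other in, say, mean glucose. It does not describe how much any one patient's glucose moves.

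The other efficacy endpoints do not fill the gap. HbA1c is an average. The HYPO score, as SAP 8.2.3 describes it, counts events with a reading under 54 mg/dL, so it does not register upward swings.

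At stake is whether the trial can report on an endpoint that it names itself, in patients described as brittle and in a study meant to support a license application. Carried out exactly as written, the plan puts variability in a table title with no variability figure beneath it. Under SAP 1, a measure chosen later would be post hoc.

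**Working it through.** The plan states no figure on this point to reproduce. The check is how far the planned outputs determine within-patient spread. The cut-points come from SAP 9.2. The means, splits and reading ranges below are assumptions for illustration.

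**Bounds for one assumed patient.** Take a mean of 120 mg/dL, with 2%, 75%, 20% and 3% of time in the four ranges and whole-number readings from 40 to 400 mg/dL. Linear programming finds the smallest and largest SD that fit. With weights w and readings g, SD = √(Σwg² − mean²).

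- *Smallest:* 2% at 59, 16% at 112, 59% at 113, 20% at 141, 3% at 201.
  - Mean: 1.18 + 17.92 + 66.67 + 28.20 + 6.03 = 120.
  - Mean square: 69.62 + 2007.04 + 7533.71 + 3976.20 + 1212.03 = 14798.6.
  - SD = √(14798.6 − 14400) = √398.6 = 20.0 mg/dL; CV = 20.0/120 = 17%.
- *Largest:* 2% at 40, 47.25% at 60, 27.75% at 140, 20% at 200, 3% at 400.
  - Mean: 0.80 + 28.35 + 38.85 + 40 + 12 = 120.
  - Mean square: 32 + 1701 + 5439 + 8000 + 4800 = 19972.
  - SD = √(19972 − 14400) = √5572 = 74.6 mg/dL; CV = 74.6/120 = 62%.

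Both patients would give the same five entries in Table 14.2.2c.

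**Dependence on the assumed range.** The lower figure uses no reading above 201, so a lower ceiling does not change it. With a ceiling of 300 instead of 400, the same construction moves 3.75% of time from 60 to 140 to keep the mean at 120. The mean square is then 32 + 1566 + 6174 + 8000 + 2700 = 18472, and SD = √4072 = 63.8 mg/dL. The gap stays wide.

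**A second assumed patient.** Mean 160 with 8/37/30/25%, readings 40-400: the smallest SD is √(27075.58 − 25600) = 38.4 and the largest √(42796.6 − 25600) = 131.1 mg/dL (CV 24% to 82%).

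**A pair inside one range.** A flat trace at 102.5 mg/dL, and a trace spending half its time at 70 and half at 135, both have mean 102.5 and 100% of time in 60-140. Their SDs are 0 and (135 − 70)/2 = 32.5 mg/dL (CV 32.5/102.5 = 31.7%). This pair does not depend on jumping across a range. A smooth sine wave between 70 and 135 also stays within 60-140 with mean 102.5, and its SD is 32.5/√2 = 23.0 mg/dL (CV 22.4%).

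**The case against.** The strongest reply is that time in four ranges is itself a coarse description of each patient's glucose distribution. Time below 60 taken with time above 200 shows excursions in both directions, which HbA1c and mean glucose cannot. This stands. The bounds above are extremes with glucose concentrated at a few values, and ordinary traces would be better separated. For example, smooth sine traces with mean 170 mg/dL and SDs of 31 and 108 spend 0/26/48/26% and 24/19/13/44% of time in the four ranges, so the planned rows would tell them apart. The planned outputs are therefore informative about spread, but they do not determine it, and within a single range they are silent.

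A reader might also infer that lability defines eligibility and is then never assessed. The documents do not support that. Protocol 4.2 mentions lability without a measure or threshold. The operative criteria in Protocol 6.4.1, beyond type 1 diabetes for more than 5 years, are "At least one episode of severe hypoglycemia in the past 3 years" and "Reduced awareness of hypoglycemia, as defined by the absence of adequate autonomic symptoms", persisting despite intensive insulin management. Severe hypoglycemia is followed in the primary endpoint and hypoglycemia severity in the HYPO score.

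Finally, SAP 9.2 attaches no hypothesis to the secondary endpoints, and the protocol and SAP agree on the list of statistics. Both points are correct and limit the weight of the finding. They do not supply the missing statistic.

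**Conclusion.** The point holds in a limited form. The endpoint named for glucose variability and hypoglycemia duration has a statistic for the second half of its name and no direct within-patient statistic for the first. In the main illustration, identical table entries allow a within-patient SD of about 20 to 75 mg/dL. That range rests on an assumed mean, split and reading range, and it is a worst case rather than a typical loss of information. The documents give no sensor data from which a typical loss could be estimated.

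It would go too far to say that the plan is blind to glucose swings, or that the trial's efficacy conclusion is in doubt. The range rows carry indirect information on spread, the endpoint is descriptive, and the primary analysis is unaffected.

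**What to change.** In SAP 9.2 and Table 14.2.2c, add the within-patient SD and CV of glucose over the 3-day recording at screening, one year after first transplant and one year after last transplant. Add the descriptive change from screening for each, which fits the interest in changes that SAP 9.2 already states. Keep the mean-glucose and time-in-range rows. Another within-patient index would also serve, provided it is fixed before analysis.

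The cost is a few more descriptive rows, with no new visits or measurements. This assumes that individual sensor readings are retained; the documents do not say whether the database holds readings or only summaries. If only summaries exist, rename the endpoint and the table to what is reported: mean glucose and time in glucose ranges, including hypoglycemia duration.

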## **10. SAFETY EVALUATIONS**

Safety analyses will be conducted for the Safety Population. Summaries will be prepared for the targeted safety endpoints listed below and for all observed adverse events (AE). All patients in the Safety population will be analyzed for safety endpoints for 1 year after the first and the last transplantation (if applicable) or up to the data cut-off date, 13 April 2015.

### **10.1. Adverse Events**

An adverse event is any unfavorable and unintended diagnosis, symptom, sign (including an abnormal laboratory finding), syndrome, or disease that either occurs during the study, having been absent at baseline, or if present at baseline, appears to worsen.

#### **10.1.1. Definitions**

The following definitions will be applied consistently to the safety analysis:

Baseline (Clinical Labs, Physical Examinations)	The baseline value will be the result collected at the immediate pre-transplant work-up visit, if scheduled, or the most recent screening visit prior to the islet transplant where the lab/examination was scheduled.
Baseline (Vital Signs)	The baseline value will be the result collected at the immediate pre-transplant work-up visit. If this assessment was not obtained, then the most recent value obtained for

	the specific parameter prior to the islet infusion will be used as the baseline value.
Baseline (ECG parameters)	The baseline value will be the most recent pre-transplant value obtained.
Change from baseline	Value at the time point – value at baseline
Treatment-emergent	Any safety assessment that occurred at the onset of or after start of the first islet infusion, up to the end of 1-year follow-up after the last infusion.

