#### **4. ANALYSIS POPULATIONS**

**ITT population:** Any patient in whom protocol-directed therapy (e.g., pre-transplant immunosuppression) is initiated will be included in the Intent-to-treat (ITT) population. All efficacy analyses will be on this ITT population regardless whether transplantation occurs or not.

**Safety Population:** Any patient in whom protocol-directed therapy is initiated will be included in the Safety population, which is the same as the ITT population. Patients in this population might not receive an islet transplant. All safety analyses will be on this Safety population.

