#### **9.1.2. Treatment of Missing Data**

The primary endpoint should be evaluable for all patients in the ITT population. However missing data can occur due to death, if the patient withdraws consent to be followed, or if immunosuppression is begun but the patient never receives a transplant. In these cases the endpoint will be classified as failure to achieve a favorable outcome. Should the endpoint not be evaluated for a patient for other reasons, a failure will be imputed unless data available at a time longer than one year after transplant indicates otherwise, in which case, that later value will be imputed.

All imputations will be reported in a patient data listing along with the reasons for imputation. The rates and the exact 95% confidence intervals for complete data and imputed data will be compared to ascertain the sensitivity of the imputation.

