#### 10.1.5. Analyses of Adverse Events

Adverse events will be coded to the Medical Dictionary for Regulatory Activities (MedDRA) preferred terms (PT) and system organ classes (SOC) using version 17.0 or higher. All tabular AE summaries will be for treatment-emergent adverse events (TEAE). For all percentages, the number of patients in the ITT population will comprise the denominator.

An overall summary table will be developed to report, across the total safety population and by number of transplants received, starting from the day of first islet cells infusion to the end of 1-year follow-up after the last transplant, the total number of events and the number and percent of patients having at least one event and those related to treatment in the following categories:

a. Procedure Related Events

The incidence and severity of adverse events related to the islet infusion procedure including:

- Bleeding (> 2 g/dl decrease in hemoglobin concentration) identified within 24 hours post transplant.

- Portal vein thrombosis, branch or main, detected by ultrasound by the end of Day 7 (or on the first visit post-transplant if it does not fall on Day 7 exactly).
- Biliary puncture identified within 24 hours post transplant.
- Wound complication (infection or subsequent hernia) identified by the end of Day 7 (or on the first post-transplant visit if it does not fall on Day 7 exactly).
- Increased transaminase levels (> 5 times upper level of normal) identified by the end of Day 30 (or on the post-transplant visit that is closest to Day 30 if it does not fall on Day 30 exactly).

b. Immunosuppression/study drug Related Events

The incidence and severity of adverse events related to immunosuppression and/or the study drug (islets), including:

- Allergy
- Reduction in GFR (> 25% reduction in estimated GFR from baseline by Cockcroft and Gault formula:

$$eC_{Cr} = \frac{(140 - \text{Age}) \times (\text{Weight in kilograms}) \times [0.85 \text{ if Female}]}{72 \times (\text{Serum Creatinine in mg/dL})}$$

- Increase in urinary albumin excretion
- New onset microalbuminuria (albumin > 30 mg/day confirmed by 24 hour urine collection) in patients who were previously within normal limits
- For those patients with baseline microalbuminuria (30-300 mg/day), new onset overt albuminuria (greater than 300 mg/day confirmed by 24 hour urine collection)
- Sensitization evidenced by increase in PRA by at least 20% relative to baseline

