- Addition or intensification of antihypertensive therapy
- Oral ulcers
- Lower extremity edema
- Gastrointestinal toxicity (diarrhea)
- Neutropenia (neutrophils < 1.3 thous/ $\mu$ L)
- Anemia (hemoglobin men < 12.1, women < 11.7 g/dL)
- Thrombocytopenia (platelets < 150 thous/ $\mu$ L)
- Infections (viral, bacterial, or fungal)
- Neoplasms, benign or malignant

c. All other TEAEs

The incidence and severity of adverse events reported outside the two aforementioned categories.

The overall summaries will also be done for the following types of AE's:

- SAEs
- TEAEs that lead to discontinuation of the study
- TEAEs resulting in death
- TEAEs graded at least 3 (severe) on the severity scale

In addition to an overall 1-year summary of AEs under each aforementioned category, a summary (number of events and the number and percent of patients having at least one event in the category) by windows of time will be provided for a respective group of AEs after the first transplant: events within the first week (by Day 7), first month (by Day 30), the first three months (by Day 90), the first six months (by Day 180), and the first year (by Day 365). The total number of patients being followed within the specific time window will be used as denominator for calculating the proportion in that time window.

In addition, summaries by SOC and PT will be developed for the following types of AE's:

- TEAEs
- TEAEs reported as related to islet transplantation
- TEAEs reported as having a severe or beyond intensity

The summaries of all TEAEs will present the number of AEs and the number and percent of patients having an AE by SOC and by specific PT. The summary of treatment-related TEAEs and the summary of severe-or-beyond (graded 3-5) AEs will only report the number and percent of patients for each SOC and PT. For the summary of AEs reported as possibly related to islet transplant, missing relationships to the treatment will be counted as possibly related to islet transplant. Likewise, if the maximum severity of an AE is not reported, then the maximum severity of the AE will be imputed.

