In addition to these summary tables, patients with treatment-emergent SAEs and patients who discontinued prematurely due to a TEAE will be presented in separate patient listings. The listings will provide all of the information reported for that AE and will include the length of time from study drug administration to the occurrence of the AE. If there are any deaths in the study, a similar listing of all TEAEs for patients who died will be provided.

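### The adverse-event window opens at the first islet infusion, but the Safety population and its denominators start at the first protocol-directed therapy

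*SAP*

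**What the plan says.** - **Population.** SAP section 4 defines Safety and ITT identically: anyone in whom protocol-directed therapy was started. It adds: "Patients in this population might not receive an islet transplant. All safety analyses will be on this Safety population". SAP 9.1.2 foresees the same case among its reasons for missing data, "if immunosuppression is begun but the patient never receives a transplant".
- **Window.** SAP 10.1.1 defines treatment-emergent as "Any safety assessment that occurred at the onset of or after start of the first islet infusion, up to the end of 1-year follow-up", where that year is counted from the final infusion.
- **Tables.** SAP 10.1.5 restricts all tabulated adverse events to treatment-emergent ones and states: "For all percentages, the number of patients in the ITT population will comprise the denominator". The exception is the summary by time since first transplant (Table 14.3.2), for which "The total number of patients being followed within the specific time window will be used as denominator".
- **Overall summary.** The same section opens the overall summary on the calendar day of the first infusion, not at the infusion itself. The Total-column footnotes in the shells start at the initial transplant.
- **Listings.** "patients with treatment-emergent SAEs and patients who discontinued prematurely due to a TEAE will be presented in separate patient listings".
- **Shells.** Tables 14.3.1 and 14.3.3 to 14.3.5 have columns for Total and for one, two and three transplants, with none for zero.

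**The concern.** The denominator and the numerator start at different times. Someone who was pre-dosed but never infused has no treatment-emergent period at all, yet counts in the Total N. Protocol 6.5.1 gives one route to this: high portal pressure confirmed at the start of the procedure rules out going on with the infusion. By then the patient has been pre-dosed and has had portal access.

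Infused patients have a gap too. Several agents are given before the islets (Protocol 6.5.2 to 6.5.4): basiliximab within two hours before, etanercept about one hour before and, in sensitized patients, a first thymoglobulin dose over the six hours immediately before. Protocol 9.2.5 and 9.2.6 describe acute hypersensitivity with basiliximab and cytokine-release reactions with thymoglobulin. Allergy heads the targeted list in SAP 10.1.5(b), which is introduced as "The incidence and severity of adverse events related to immunosuppression and/or the study drug (islets), including". Protocol 6.9.1 collects non-serious events from hospitalization for the first transplant, so these reactions are recorded, but under 10.1.1 they are not tabulated.

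At stake are the rates in the main safety tables of a trial meant to support a license application. SAP 2.9, which lists changes from the protocol analysis, does not mention the mismatch.

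**Working it through.** The documents give no figure for this point, so there is none to reproduce. The check compares the rules and then sizes the effect.

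**Step 1: who can be counted.**

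| Patient or event | In Total N? | Can enter a TEAE numerator under 10.1.1? |
|---|---|---|
| Infused, event after infusion starts | Yes | Yes |
| Infused, event between first pre-transplant dose and first infusion | Yes | No |
| Never infused, any event | Yes | No |

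**Step 2: does the day-based wording in 10.1.5 close the gap?** Only in part. Read alone, it could admit same-day pre-infusion events in infused patients to the overall summary. It does not reach events on an earlier calendar day or any event in a never-infused patient. The same section still limits its tables to treatment-emergent events, which leads back to 10.1.1. The two passages conflict.

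**Step 3: size.** For one type of event, let N be all treated patients, a the patients with the event inside the window, and b the patients whose only event of that type lies outside it (never infused, or infused with a pre-infusion event only).

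- Reported share = a/N
- Share over all treated patients = (a + b)/N
- Understatement = (a + b)/N − a/N = b/N

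The documents do not give b, so these values are assumptions. N = 50 is the planned number. N = 15 is the smallest size in SAP Table 1, and SAP 2.8 discusses a sample that small.

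| b | N = 50 | N = 15 |
|---|---|---|
| 0 | 0 | 0 |
| 1 | 1/50 = 2.0 points | 1/15 = 6.7 points |
| 2 | 2/50 = 4.0 points | 2/15 = 13.3 points |

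The effect cannot be negative: as written, the rule lowers a Total-column percentage or leaves it unchanged.

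**Step 4: reach.** Pre-dose reactions before a second or third infusion come after the first infusion began, so they are inside the window. The gap concerns the first transplant only.

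**The case against.** The best case for leaving the plan alone has four parts.

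- **Anchoring at infusion is a reasonable design choice.** The islets are the product. Protocol 6.10.1 follows for safety those who receive a transplant, and Protocol 6.10.3 analyzes the same group. This stands as an argument for an infused-only denominator. It does not support an infusion-based window over a wider denominator.
- **The interval is short.** The excluded time is mostly hours, and thymoglobulin goes only to sensitized patients at the initial transplant. Recipient exclusion 21 narrows that group further, and its size is not given. This stands and limits the likely size. Reactions that begin after infusion starts are counted in any case.
- **Nothing captured is hidden.** SAP 3.1 lists all data in the database, and listing 16.2.7a covers adverse events. This also stands, but a listing does not correct a tabulated rate. Protocol 6.12.1 also ties completion of a case report form to undergoing transplantation, so a never-infused patient's events might not be captured.
- **The effect may be nil.** If b is zero, no rate is understated. That is correct.

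A reader might infer more: that each never-infused patient by itself biases the rates downward. The documents do not support that. Among all treated patients, someone with no event belongs in the denominator and adds nothing to the numerator, so a/N is right for that patient. The bias needs an actual event outside the window.

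A reader might also take the loss of every pre-infusion event as settled. It is not, because the day-based wording in 10.1.5 can be read the other way for the overall summary.

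**Conclusion.** The mismatch is real and follows from SAP 4, 10.1.1 and 10.1.5 taken together. Never-infused patients are in the Total denominators of Tables 14.3.1 and 14.3.3 to 14.3.5 with no possibility of being in a numerator. Under 10.1.1, events before the first infusion are also missing from the treatment-emergent tables and from the serious-event and discontinuation listings. The definition and the day-based wording must be reconciled.

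The understatement over all treated patients is b/N: 2.0 points per affected patient at N = 50, and zero if no one is affected. It depends on b and on the number never infused, neither of which the documents give, so no actual bias can be claimed. This is a definition to correct before the safety tables are run. It is not evidence that the safety profile is misreported.

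**What to change.** **Change.** For adverse events only, define treatment-emergent as onset or worsening on or after the first dose of protocol-directed therapy. Close the window one year after the last infusion or, for a never-infused patient, at the end of follow-up or the 13 April 2015 data cut-off. Use this definition in SAP 10.1.1, throughout 10.1.5 including the serious-event and discontinuation listings, and in the table footnotes. Add a zero-transplant column to Tables 14.3.1 and 14.3.3 to 14.3.5. SAP 10.2 already starts study concomitant medications at the initiation of protocol-directed therapy, so the anchor is not new to the plan.

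Keep the infusion anchor for laboratory values, vital signs and ECG. Their baselines are taken before the transplant, and an earlier start could make one value both baseline and treatment-emergent.

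**Alternative.** Keep the infusion anchor for adverse events, use infused patients as the denominator of the treatment-emergent tables, and tabulate pre-infusion and never-infused events separately.

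**Either way,** confirm that adverse events are captured for never-infused patients, given Protocol 6.12.1.

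**Cost.** The first option needs one added definition, matching wording and footnotes, and one column in four tables. For infused patients the data are already collected from hospitalization. For never-infused patients, source records may be needed. Reported adverse-event rates may be slightly higher.
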